TITLE: A Pilot Study on the safety and efficacy of Mifepristone for the prevention of relapses of alcohol drinking

PI: [name]

NCT02243709

IND121984

DATE: December 15 2014

CLINICAL PROTOCOL

A Pilot Study on the safety and efficacy of Mifepristone for the prevention of relapses of alcohol drinking

Principal Investigator:

[name], PhD

Brown University, Providence, RI

[contact]

[contact]

PROTOCOL SYNOPSIS

Objective: The primary objectives of the study include: A) Establish the safety and tolerability of using 600mg of mifepristone and 32.4mg yohimbine while consuming alcohol; and B) Demonstrate the feasibility of the study design and obtain an effect size to estimate a sample size for an appropriately powered larger R01 application using mifepristone and yohimbine together when administering alcohol.

Rationale: Glucocorticoids (GC) mediate adaptation to stress and regulate termination of the stress response through the hypothalamic–pituitary–adrenal (HPA) axis feedback action. The link between stress and chronic relapsing alcohol-use disorders (AUD) and substance-use disorders (SUD) has long been established in the addiction research field. Preclinical studies show the GC-receptor antagonist, mifepristone, reduces behavioral hyperexcitability during the acute phase of alcohol withdrawal, suggesting that mifepristone is a promising pharmacotherapy for alcoholic individuals to reduce the cognitive deficits caused by chronic alcohol use and withdrawal symptoms. In our preclinical studies, we showed that in conditions where stress is limited, mifepristone has no effect on alcohol intake, corroborating the hypothesis that GC blockade represents a key element in the preoccupation/anticipation (craving) stage of the addiction cycle. However, what remains unknown is the role of mifepristone in stress-induced craving and relapses of alcohol drinking in humans.

Overview of Study Design: The design will be a randomized within, crossover, double-blind, placebo-controlled human study with mifepristone in non-treatment-seeking-alcohol-dependent individuals. The study will be conducted in consecutive phases (Figure 1):

Visit#1: Screening;

Visit#2: Randomization and drug/placebo dispensed (for seven days);

Visit#3: First lab-session: single dose of yohimbine;

Visit#4: Washout period, follow-up (one month) and drug/placebo dispensed (for seven days);

Visit#5: Second lab-session, single dose of yohimbine; Motivational session (MET);

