Medications and doses: Participants receive an oral dose of 600 mg of mifepristone or matching placebo for approximately seven days (plus three extra pills). Participants will receive detailed information on the study medications, including their current use and possible side effects. Mifepristone treatment in clinical setting has shown to be safe, tolerable, and acceptable⁸⁷⁻⁸⁹, including in participants suffering from depression, anxiety, and PTSD⁹⁰⁻⁹². On Days 7 and 44, all participants will receive a single oral dose of 32.4 mg yohimbine approximately one hour ($t_{max}=1$ hour) prior to the lab session. The oral dose of yohimbine for this study is based on prior studies in which yohimbine was administered to examine neuroendocrine probe in human studies^{57,93,94}. Ample data support the safe use of yohimbine to induce craving in alcohol-dependent individuals⁵⁷, and the safe induction of stress in PTSD veterans⁹⁵ and gamblers⁶⁰. We already obtained the Investigational New Drug (IND#121984) from FDA that determined that the clinical investigation of mifepristone and yohimbine while consuming alcohol is safe to proceed (see attaché letter form FDA). Our IND was also cross-referenced by the IND of Corcept Therapeutics (IND#059737) for chemistry, manufactory, pharmacological, and toxicology data of mifepristone (see attached letter form Corcept). Participants will receive detailed information on the study medications, including their current use and possible side effects.

STUDY PROCEDURES:

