Alcohol Self-Administration (ASA). Participants are presented with a priming dose of alcohol designed to raise blood alcohol levels to 0.03 g/dl. Consistent with previous studies^{78,103,104}, we will wait 40 minutes before presenting more alcohol. We will assess craving and whether stress-induced craving will modify responses to the priming drink using the ACQ. Stimulant and sedative effects of alcohol will be assessed using the Biphasic Alcohol Effects Scale (BAES)¹⁰⁵. The "free-choice" phase of the ASA lasts 120 min and the ACQ will be

administered every 30 min^{78,103,104,106}. Each participant will get \$3.00 per drink (max possible is \$24), provided as an alternative reinforcer for not drinking. Each beverage is calculated to raise the blood alcohol levels by 0.015g/dl. If the participant's BrAC has reached 0.1, then the alcohol consumption period will stop. We will also collect multiple BrAC values in order to monitor the mifepristone effects on alcohol pharmacokinetic and pharmacodynamic levels. Participants wait until BrAC = 0.00 (repeated twice) before being discharged. At the end of Visit 5, a Motivational Enhancement Therapy (MET) will be performed to provide education about alcoholism and to explore participants' desire to get treatment if they wish to receive it, and then we will assess at last follow-up to ascertain that drinking has not increased.

Participants are strongly encouraged to remain in the lab until no longer intoxicated. After the laboratory session, we will provide food and water and they can watch television. If they want to leave, we will provide a taxi ride.

Compensation: sessions will last approximately 6 hours, and subjects will receive \$100 for participation plus another possible \$3/drink as incentive for not drinking (max \$24).

Washout period: During the washout and follow up period (30 days, plus or minus two days to accommodate the schedule of the next visit) we will contact participants weekly by telephone to ensure that there are not unexpected side effects. We will alert the study physicians in the event of anxiety, depression and suicidality. We will also send a text reminder for the next visit (Visit #4 and Visit #6).

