This study will represent the first intervention of mifepristone on yohimbine-induced alcohol craving and consumption in this population. As this is a safety and tolerability study, adverse events evaluation (AEE) will be reported as the number and their intensity. We will compare the number and intensity of AEE in the mifepristone vs. placebo groups weekly and during the alcohol laboratory sessions. These events will be rated as none, mild, moderate, and severe. Paired *t*-tests will be used to test for medication effects. Generalized Estimating Equations (GEE) will be used for dichotomous data if events are rare. To guard against Type II errors, we will also report additional descriptive data on adverse events (the distribution of the maximum level of an adverse event collapsed across time points per condition). This study integrates self-reported and clinician-administered assessments with clinical laboratory analysis. A series of analyses of covariance (ANCOVA) will be conducted to test the effect of mifepristone on alcohol craving while controlling for variance

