Center Alcohol and Addiction Studies

Brown University

TITLE: A Pilot Study on the safety and efficacy of Mifepristone for the prevention of relapses of alcohol drinking

PI: [name]

NCT02243709

IND121984

DATE: December 15 2014

Statistical analysis

Distributional characteristics of outcome measures were examined to evaluate similarity to the normal distribution, detailed descriptive analysis of demographics, substance use, and clinical characteristics were conducted. Comparisons with these characteristics, in relation to enrolled versus completer status, were performed using *t*-tests to analyze continuous variables (e.g., age) and Chi square (χ^2) for categorical variables (e.g., sex, race, smoking status). Attrition rates between the screening visit and follow-up visit were examined descriptively to assess for potential bias. In addition, a logistic regression was performed to test for possible bias due to period (A/B: placebo first, then mifepristone and B/A: mifepristone first, then placebo) or medication carryover (1: placebo and 2: mifepristone), as done in our prior cross-over trial¹.

Primary outcomes: safety and tolerability of oral administration of mifepristone was assessed after 7 days in outpatient setting, and when it was administered with yohimbine and alcohol during the laboratory paradigms. These analyses included comparing the number of adverse events (AEs) between the mifepristone and placebo condition via a χ^2 test. The results were presented using summary statistics such as number of subjects (*n*); mean (*M*); standard deviation (*SEM*) or frequency distributions (%).

Primary outcomes: safety and tolerability assessed by the number of adverse events (AEs) of oral administration of mifepristone was assessed after 7 days in an outpatient setting, and when it was administered with yohimbine and alcohol during the laboratory paradigms. Additional safety and tolerability analysis included hemodynamic response, alcohol pharmacokinetics, and subjective effects of alcohol between the mifepristone and placebo condition (χ^2 test).

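### The primary adverse-event test estimates what mifepristone adds, but Objective A concerns the whole mifepristone + yohimbine + alcohol combination, whose event rate has no interval and no stated role in the conclusion

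*SAP*

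**What the plan says.** **Objective.** The protocol synopsis sets Objective A as "Establish the safety and tolerability of using 600mg of mifepristone and 32.4mg yohimbine while consuming alcohol". Aim 1 repeats it, and the SAP's Power section restates it.

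**Exposure in the laboratory.** Under Medications and doses: "On Days 7 and 44, all participants will receive a single oral dose of 32.4 mg yohimbine". Under Alcohol Self-Administration, for both laboratory visits: "Participants are presented with a priming dose of alcohol designed to raise blood alcohol levels to 0.03 g/dl". A 120-minute free-choice drinking phase follows. By design, only mifepristone versus placebo differs between sessions.

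**Primary AE analysis.** Under Primary outcomes the SAP states "These analyses included comparing the number of adverse events (AEs) between the mifepristone and placebo condition", by a chi-square test. The outcome covers two settings; it "was assessed after 7 days in outpatient setting, and when it was administered with yohimbine and alcohol during the laboratory paradigms". The further primary safety analyses (hemodynamic response, alcohol pharmacokinetics, subjective effects) are also mifepristone-versus-placebo contrasts. Frequency distributions are listed as generic summary statistics, with no interval.

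**Descriptive AE reporting.** The protocol's Data analysis section says "We will compare the number and intensity of AEE in the mifepristone vs. placebo groups weekly and during the alcohol laboratory sessions", with events rated none, mild, moderate or severe. As a guard against Type II errors it adds a descriptive report of "the distribution of the maximum level of an adverse event collapsed across time points per condition". The Sources of materials section also says that AE number and intensity will be reported.

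**Decision language.** The SAP's Power section ties the primary safety outcome to a difference in AEs and mentions noninferiority. It gives no margin, one-sided bound or AE rate. Tests are two-tailed at 0.05.

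**The concern.** The objective asks about an absolute quantity: how well people tolerate the three agents together. The named test concerns a relative one: whether AEs are more frequent with mifepristone than with placebo, on a background that already contains yohimbine and alcohol. AEs that this background causes by itself are expected on both sides and contribute little or nothing to the difference.

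The documents offer no other reference for that background. No laboratory session omits yohimbine; a preliminary yohimbine-only step is discussed under Alternative Design Considerations and not adopted. The AE table lists the two drugs separately and leaves yohimbine's frequencies undefined.

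Two equally poorly tolerated sessions would give a null test. The pilot is also meant to supply safety data for a larger trial, which needs the event rate on the combination and its uncertainty. As written, that rate would be at most a descriptive figure without an interval.

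**Working it through.** **The plan's own figure.** The SAP gives N=32 (originally 20) with no AE rate, difference, power or margin, so it cannot be reproduced for the AE outcome. The protocol expects 50 completers. All three sizes are used below. Every AE rate is an assumption, because the documents give none for the combination. The unit is the participant with at least one event of the stated type.

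**1. What the contrast contains.**

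| Source of AEs | Mifepristone session | Placebo session | Seen in the difference? |
|---|---|---|---|
| Yohimbine, alcohol, or both, without mifepristone | yes | yes | No, apart from any difference in free-choice intake |
| Mifepristone alone | yes | no | Yes |
| Mifepristone interacting with yohimbine or alcohol | yes | no | Yes |

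In the outpatient week there is no yohimbine dose, so that comparison describes mifepristone without it.

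**2. Response of the test to shared risk.** Let a and b be the numbers affected in each condition, each Binomial(n, p) with the same p, treated as independent (as an ordinary chi-square does). With p̄ = (a+b)/(2n), the statistic is X² = ((a−b)/n)² / (p̄(1−p̄)·2/n). The probability of a null result is the sum of the joint probabilities over all pairs with X² < 3.84. At n=32:

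| Shared true risk | 5% | 10% | 30% | 50% | 70% | 90% |
|---|---|---|---|---|---|---|
| P(not significant) | 0.97 | 0.94 | 0.95 | 0.94 | 0.95 | 0.94 |

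A null result is about as likely when nearly everyone has an AE as when few do. Positive within-person correlation would make it more likely still with an unpaired test.

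**3. Even the added effect is poorly resolved.** Normal-approximation power is Φ[(d − 1.96·s₀)/s₁], where s₀ = √(2p̄(1−p̄)/n) and s₁ = √((p₀(1−p₀)+p₁(1−p₁))/n). Example: n=32, p₀=0.30, p₁=0.50 gives s₀=0.1225, s₁=0.1199 and power Φ(−0.33)=0.37. Over placebo rates of 5% to 70%, power at n=32 is 0.12 to 0.26 for a 10-point increase and 0.37 to 0.62 for a 20-point increase.

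**4. What addresses Objective A.** The exact (Clopper-Pearson) two-sided 95% upper limit with zero events is 1 − 0.025^(1/n):

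- n=20: 1 − 0.025^(1/20) = 16.8%
- n=32: 1 − 0.025^(1/32) = 10.9%
- n=50: 1 − 0.025^(1/50) = 7.1%

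**5. Illustration only.** If 16 of 32 were affected in each session, the difference would be 0. The rate on the combination would be 50%, exact 95% interval 31.9% to 68.1%.

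**The case against.** The strongest reply is that the protocol already guards against this. It leads with AE number and intensity, separates the weekly period from the laboratory sessions, and adds maximum severity per condition because a test might miss harm. Serious AEs are classified and reported individually, and aggregate safety is reviewed every 10 weeks with termination among the possible outcomes. Anyone with n and N can compute an interval. This stands: a reader might infer that the plan reports no absolute AE figures or that shared harm would go unseen, and the documents do not support that.

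It can also be said that the contrast is relevant to the combination. Interaction AEs arise only with mifepristone and do not cancel, and interactions are a safety question the protocol raises itself. The SAP also words its primary outcome around mifepristone, including when given with yohimbine and alcohol. This stands too: the test addresses part of the objective. Nor need background AEs cancel exactly, because only the priming drink is fixed; if mifepristone changes drinking, alcohol-related AEs may differ.

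Finally, no passage says that a non-significant test will be read as showing safety. That is an inference a reader might draw from the absence of any other criterion, not a stated rule.

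What the reply leaves open is that the descriptive figures have no interval and no stated role in the Aim 1 conclusion, and that the SAP's AE outcome is number only, without severity. The noninferiority wording does not fill the gap: it has no margin, and a margin would bound only mifepristone's added effect.

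**Conclusion.** The concern holds in this form: the named primary AE test does not estimate the quantity in Objective A, and the planned figures that could do so are not given an interval or made the basis of the conclusion. A null result on a two-sided test without a margin cannot establish that the combination is safe.

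The conclusion about what is estimated rests on the design and needs no assumed rate. The null-result probabilities and power figures rest on assumed AE rates, participants as the unit and independent conditions. The zero-event limits depend only on n and a binomial count; at the SAP's N=32, no observed events would still be compatible with a true risk of up to 10.9%. The 16-of-32 case shows the logic and is not a forecast.

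This should be changed. It alters what the pilot can claim for its primary objective, but it does not undermine the design or the data collection.

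**What to change.** In the SAP, under Primary outcomes:

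1. Make the primary Aim 1 laboratory result the proportion of participants with any AE, a moderate-or-severe AE and a serious AE in the mifepristone + yohimbine + alcohol session, each with an exact 95% confidence interval. Show the same figures for placebo + yohimbine + alcohol beside them.
2. Report AEs from the 7-day outpatient periods separately, by condition, as information on mifepristone without yohimbine.
3. Keep the mifepristone-placebo difference, analysed as paired and with its interval, as the estimate of mifepristone's added effect. Note that it includes any effect through free-choice alcohol intake.
4. State that a non-significant difference is not evidence that the combination is safe. Remove the noninferiority wording, or define a margin and say that it concerns only the added effect.

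The cost is SAP wording and one table from data the protocol already collects, including severity. The downside is a less favourable safety statement: at N=32 an upper limit near 11% must be shown even with no events.

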Visit#6: Follow-up (one month); END of STUDY.

Study Population: Sixty-five non-treatment-seeking, alcohol-dependent participants will be recruited. Fifty-eight participants will be enrolled for screening with **50 participants (n = 50)** expected to complete the study. Participants will primarily be recruited via advertisements placed in local newspapers and posted on buses.

Safety Measurement/Parameters: Risks of medication side effects will be minimized through careful and detailed screening of participant. Signs of anxiety and stress, adverse events and vital signs will be assessed at each visit by psychometric assessments. Safety laboratory tests will be evaluated at baseline, and at the end of the study participants will receive a behavioral motivational session at the end of Visit 5.

Financial considerations: There will be no cost(s) to participate in this study. The study medications and all procedures that are not part of routine care, but are required for the study, will be provided to the participant. If eligible for the study, participants will receive \$25 for the randomization visit (Visit# 2) and for the follow-up visits (Visits #4 and #6). During the laboratory phase, at each visit (Visits #3 and #5) participants are compensated \$100 + another possible \$3/drink as incentive for not drinking (max \$24). Therefore, each participant may be compensated up to \$323 during the entire study period. Participants will be also compensated for their travel costs.

Specific Aims:

Aim 1: to assess the safety and tolerability of mifepristone and yohimbine while consuming alcohol.

Aim 2: to test the hypothesis that an increase in alcohol craving induced by yohimbine is antagonized by pre-administration with mifepristone.

Aim 3: to test the hypothesis that an initial priming drink and alcohol consumption induced by yohimbine is antagonized by pre-administration with mifepristone.

TABLE OF CONTENTS

PROTOCOL SYNOPSIS	2
TABLE OF CONTENTS	3
SPECIFIC AIMS	4
RATIONALE AND SIGNIFICANCE TO THE ALCOHOL FIELD	5
Stress and alcohol dependence	5
Clinical relevance	5
Pharmacological stress targets	5
Mifepristone	5
Stress-induced models	6
Integration: psychoneuroendocrinology and trauma factors	6
Significance for NIAAA	6
Innovation	6
The Investigator Team	7
The qualified medical personnel during the laboratory sessions	7
RESEARCH DESIGN AND METHODS	8
Overview of Proposed Research	8
Medications and Doses	8
Study Procedures	9
Data Analysis Plan	10

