Translating preclinical paradigms into effective models for assessing pharmacological approaches for stress-induced alcohol relapse in humans requires a comprehensive model capable of integrating: alcohol-proximal variables that influence drinking (withdrawal symptoms, craving), neuroendocrine variations (cortisol), and stress-risk factors (different temporal traumatic events). A comprehensive stress model is needed because emotional distress, neuroendocrine activation, stress-related genetic variations, craving, and alcohol consumption do not necessarily overlap in alcohol-dependent individuals. Mifepristone may be a valuable pharmacotherapeutic strategy for preventing relapse to AUD, and yohimbine is a pharmacological stressor capable of increasing craving, creating recall of traumatic memories, and altering neuroendocrine levels in alcohol-dependent individuals. As FDA-approved medications, both mifepristone and yohimbine have the advantage of being directly applicable to an alcohol clinical setting and being utilized in the translational efforts described in this application.

The overall objective of this study is to conduct a randomized pilot laboratory study consisting of a placebo-controlled assessment of the effects of 600 mg of mifepristone for a week, in a stress-induced condition triggered by a single dose of 32.4 mg of yohimbine in non-treatment-seeking-alcohol-dependent individuals. In the following specific aims, I propose:

Aim 1: to assess the safety and tolerability of mifepristone and yohimbine while consuming alcohol. Randomized participants will complete two alcohol laboratory sessions along with a battery of physiological and psychological assessments that measure adverse events and pharmacokinetic (PK)/pharmacodynamic (PD) interactions.

Aim 2: to test the hypothesis that an increase in alcohol craving induced by yohimbine is antagonized by pre-administration with mifepristone. To test this hypothesis, we will establish the effect of mifepristone on alcohol cue-elicited craving during a cue-reactivity (CR) experiment along with a series of physiological and psychological tests assessing alcohol craving.

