Innovation. This research is innovative in three ways. First, it focuses on a novel target for the prevention of alcohol relapse, the stress system. The second major innovation of this proposal is the development of a translational research clinical model that integrates administration of pharmacological stressors with alcohol

laboratory study methods developed from personal neuroscience and neuropharmacology knowledge. As the design of this project has built logically on our prior work, it is our intent to translate our neuroscience safety results to clinical research, which includes examining the effects of pharmacokinetic (PK) interactions (alcohol, yohimbine, mifepristone) on Pharmacodynamics (PD) additive responses (CNS depressant properties of alcohol or increased sedation/depression of respiratory and/or cardiac functions). Although not observed in our preclinical models, possible negative outcomes may be observed in stress-induced conditions in alcohol-dependent individuals, such as potentiation of the stimulant phase of alcohol, increase in behavioral effects of alcohol intoxication, or worsening alcohol withdrawal syndrome. Our strong team includes well-established clinicians in the fields of experimental pharmacotherapeutics in alcohol laboratory studies, psychiatry and neuropsychopharmacology, to ensure safety and answer additional clinical questions that may arise during or between alcohol laboratory sessions. This interdisciplinary-validated human laboratory protocol is critical to determine safety and tolerability of stress-induced pharmacological procedures before moving forward into a larger randomized clinical trial and to pave new hypotheses to be explored in alcohol and stress neuroscience research. Finally, by providing safety measures and PK/PD data, this proposed application will pave the way for new therapeutic targets that could be utilized in other stress/anxiety mental disorders that have high comorbidity with AUD.

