Visits 3 and 5 (Stress-induction and Alcohol Laboratory Session): All procedures and responsibilities of each member of the research team are described in Appendix Z (page 3 and 5). Participants will be instructed not to consume alcohol for 24 hours and must have a BrAC of 0.00 prior to any assessment. A sample of salivary cortisol will be collected and a single oral dose of 32.4 mg yohimbine will be administered to participants. The lab-session will begin one hour later in order to allow yohimbine to take effect⁹⁶, at which time a second sample of cortisol will be collected. The CR will be run first, followed by the ASA (Assessments Schedule, Appendix Z). The PI will schedule Visit #3 and Visit #5 (alcohol laboratory sessions) only if [name] will be in proximity of CAAS laboratory. The PI will not schedule Visit #3 and Visit #5 if both study physicians are traveling or not in Providence.

Cue-reactivity (CR). The CR will be similar to previously published studies^{73,97-101}. The entire procedure takes about 45 minutes. The water trial provides a controlled baseline that controls for all aspects of stimuli and movement, except for the nature of the beverage. Next, participants will undergo two 3-minute alcohol cue exposure trials that will be identical to the water trial except that the glass of water will be replaced with their preferred alcoholic beverage and the bottle of water will be replaced with the appropriate commercially-labeled alcohol bottle. After every 3-minute beverage exposure, participants will rate their urge to drink alcohol by completing the alcohol urge and craving questionnaire (ACQ) to assess attention to the sight and smell of water and alcohol cues. Saliva (weight in cotton rolls, mg), heart rate (HR; beats/min) and blood pressure (systolic, diastolic, and mean arterial pressure-MAP) will be monitored continuously using a Dinamap Adult Vital Signs Monitor. After the conclusion of the CR, participants will undergo the ASA. Consistent with recommendations¹⁰², participants will be informed they will receive alcohol following the CR. The last of salivary cortisol (by spitting in a tube) will be collected at the end of the CR.

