Secondary outcomes: Craving measures included alcohol craving questionnaire short form-revised (ACQ-SF-R)². Values of the water trials for each dependent variable were inserted as covariate in the model (allowed for the dependent variable to be specific for alcohol), time coded: t_1 =alcohol trial 1 and t_2 =alcohol trial 2. In the bar laboratory, alcohol consumption was measured by number of drinks consumed (*t*-test). In the outpatient setting, alcohol consumption was measured by self-report using the timeline follow back method, reported as heavy drinking days and drinks per week.

All statistical analysis was performed after participants had their follow-up visit and the study database had been locked. All the statistical procedures were performed by IBM SPSS Statistics for Windows, version 27 with Macro MEMORE extension⁹ (IBM Corp., Armonk, NY, USA) and GraphPad Prism (v.5) was used to generate figures (La Jolla, CA, USA). The effect sizes were calculated as η^2 for GLM and Cohen *d* for *t*-test. All statistical tests were two-tailed, and statistical significance was accepted if an alpha value $p<.05$ was obtained.

For all outcomes, we utilized an intention-to-treat (ITT) approach, where participants were examined based on their *a priori* randomized protocol and received at least one dose of the study medication

(mifepristone or placebo)³. All analyses were conducted using Generalized Estimating Equations (GEE)⁴ with robust standard errors, and an unstructured correlation matrix, unless noted.

Power

This was a proof-of-concept trial to demonstrate the feasibility of the combined study design, the safety and tolerability of mifepristone and yohimbine while consuming alcohol, and the potential value of testing mifepristone in an appropriately-powered larger RCT. In selecting a target sample size, we balanced power considerations and feasibility given the translational nature of this trial. Because of the within-subjects design, power to test the effects of study drug is optimized for this modest sample size (originally $N=20$ then, after additional funding, increased to $N=32$). For the safety and tolerability outcomes (primary) adverse events difference was detected based on a judgement concerning the minimal effect which has clinical relevance in the management of patients. In a noninferiority trial, the exact sample size cannot be fixed in advance because it depends upon the chosen stopping guideline⁵.

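### Of the AE measures the SAP carries over only the number, not the intensity, and neither document plans a by-condition comparison of the withdrawal, anxiety or depression scales

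*SAP*

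**What the plan says.** The Protocol makes safety and tolerability its first primary objective and Aim 1.

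- Synopsis, Safety Measurement/Parameters: "Signs of anxiety and stress, adverse events and vital signs will be assessed at each visit by psychometric assessments".
- Aim 1: participants complete two laboratory sessions "along with a battery of physiological and psychological assessments that measure adverse events" and pharmacokinetic/pharmacodynamic interactions.
- Innovation: the possible negative outcomes include "increase in behavioral effects of alcohol intoxication, or worsening alcohol withdrawal syndrome".
- Psychosocial assessments: CIWA is done at every session before any procedure. HAM-A and HAM-D are described as research outcomes as well as monitoring tools. Several scales carry a score that triggers a call to the study physician.
- Data analysis: "We will compare the number and intensity of AEE in the mifepristone vs. placebo groups weekly and during the alcohol laboratory sessions". Events are graded from none to severe, and the distribution of each condition's maximum AE level is to be described. Sources of materials repeats the commitment to number and intensity.

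The SAP, under Primary outcomes, states: "These analyses included comparing the number of adverse events (AEs) between the mifepristone and placebo condition via a" chi-square test. It then continues: "Additional safety and tolerability analysis included hemodynamic response, alcohol pharmacokinetics, and subjective effects of alcohol". Intensity is not mentioned. CIWA, HAM-A, STAI and HAM-D are not mentioned either.

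**The concern.** A count treats all events alike. Two conditions with the same number of AEs, one with only mild events and the other with several severe ones, give the same result on the SAP's comparison. The Protocol's graded comparison would separate them.

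The scales raise a related problem. A shift in withdrawal, anxiety or depression scores that nobody records as an AE would not be compared between conditions at all. Alert thresholds protect the individual participant, but they do not estimate a drug effect. The pilot is meant to support a larger trial, so a tolerability statement with no mifepristone-versus-placebo estimate for a named harm, and none for a listed safety parameter, leaves a gap that data the trial collects anyway could partly fill.

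**Working it through.** There is no stated figure to reproduce. The main check sets the texts side by side; the arithmetic then shows what the added estimates could deliver.

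**1. What is planned as a mifepristone-versus-placebo safety comparison**

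| Measure | Protocol, Data analysis | SAP |
|---|---|---|
| AE number | yes | yes (chi-square) |
| AE intensity | yes, plus maximum level | not mentioned |
| CIWA | none | none |
| HAM-A, STAI-state | only as covariates for craving | none |
| HAM-D | none | none |

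Of two AE measures, the SAP keeps one. Of four scales, neither document compares any. The SAP's default model (GEE with robust standard errors) settles how outcomes are analysed, not which ones. The one Protocol sentence about comparing anxiety (Yohimbine section) describes a baseline-to-release check on the participant, not a drug contrast.

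**2. What each scale can show**

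- *Pre-procedure CIWA at Visits 3 and 5.* For these visits, "Participants will be instructed not to consume alcohol for 24 hours". CIWA precedes yohimbine and study alcohol, so it reflects withdrawal after about a week of study drug, not the three-way combination. The same reading applies to pre-procedure HAM-A and HAM-D.
- *End-of-session HAM-A and STAI-state.* From dosing to the end of free choice is 60 + 45 + 40 + 120 = 265 minutes, or 205 minutes (3.42 h) after the stated one-hour tmax. With the stated half-life of 1 to 2 h, and assuming simple exponential decline from peak, 2^(-3.42/1) = 9% to 2^(-3.42/2) = 31% of peak yohimbine remains. The score also follows drinking that the participant chose. If a single study baseline B is used, it cancels: (post-mifepristone − B) − (post-placebo − B) = post-mifepristone − post-placebo. A change score therefore adds information only if each session has its own pre-yohimbine value.

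**3. Precision of a score difference**

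Inputs: n = 20, then 32 (SAP, Power) and 50 expected completers (Protocol synopsis). The documents give no SD or correlation, so results are in SD units over an assumed between-session correlation ρ, with equal SDs, complete pairs and no allowance for the period term.

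Half-width = t(0.975, n−1) × √(2(1−ρ)/n)

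- n = 32: 2.04 × √(1.4/32) = 0.43 at ρ = 0.3; 2.04 × √(1.0/32) = 0.36 at ρ = 0.5; 2.04 × √(0.6/32) = 0.28 at ρ = 0.7.
- At ρ = 0.5: 0.47 for n = 20 and 0.28 for n = 50.

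For a within-session change, the variance of the difference is 4(1−r_w)(1−r_c). Assuming a pre/post correlation r_w of 0.5 to 0.7 and a between-session correlation of changes r_c of 0 to 0.5, it runs from 0.6 to 2.0, giving half-widths of 0.28 to 0.51 SD at n = 32.

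**4. What an alert table can exclude**

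With no crossings, the two-sided 95% upper limit is 1 − 0.025^(1/n): 16.8% at n = 20, 10.9% at n = 32 and 7.1% at n = 50.

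**The case against.** The best defence is that these scales have another job. The Psychosocial assessments section says they serve eligibility and safety during the trial, with call thresholds, and Aim 1 describes its battery as measuring AEs, which the Protocol does compare. Restlessness and nervousness are scored items on the Side Effects Report Form, so some anxiety reaches the AE data. The SAP's wording is inclusive, and nothing in it withdraws the Protocol's intensity comparison. This stands, and it limits the point to incompleteness. It does not remove it: an open list specifies no analysis, and the Protocol itself calls HAM-A and HAM-D research outcomes.

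It is also fair that pre-procedure CIWA is a weak instrument here. Entry requires a low score and removal follows at 7 or above, so the range is narrow. The exact timing of HAM-A, STAI and HAM-D sits in Appendix Z, which is not among the documents.

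Three stronger readings should be resisted.

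- A reader might infer that the SAP's safety analysis is an AE count and nothing else. It also lists hemodynamics, alcohol pharmacokinetics and subjective alcohol effects, the last of which reasonably covers the stimulant and intoxication harms named in the Protocol.
- A reader might infer that score comparisons would be far more powerful than AE comparisons. The documents give no SD, correlation or AE rate, so any such contrast would follow from whatever was assumed about how AEs relate to scores.
- A reader might infer that the added scale contrasts would measure harm from mifepristone, yohimbine and alcohol together. As step 2 shows, pre-procedure scores cannot, and end-of-session scores are mixed with self-chosen drinking.

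**Conclusion.** The point holds as an incomplete primary safety analysis, not an invalid one. The dropped AE intensity is a plain difference between Protocol and SAP and rests on no assumption. The missing scale comparisons are a gap relative to what the Protocol lists as safety parameters, possible harms and research outcomes. The change is worth making because it is cheap and would show differences in severity or score that a count hides.

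The gain is modest. At n = 32 a score difference would be known to about ±0.28 to ±0.43 SD under the assumed correlations, and an empty alert table would still be compatible with a rate of up to 10.9%. These figures describe; they would not establish tolerability. Confidence is moderate, because the assessment schedule is unseen.

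**What to change.** In the SAP's safety section:

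1. Restore the Protocol's AE intensity comparison beside AE number, including the maximum grade per participant and condition.
2. Tabulate by condition the participants crossing each physician-alert threshold and those removed for CIWA of 7 or above.
3. Report descriptively, with 95% CI and a period term, the mifepristone-minus-placebo difference in pre-procedure CIWA at Visits 3 and 5, and in pre-procedure HAM-A and HAM-D where the schedule has them. Use all available sessions and keep any CIWA score that triggered removal, since dropping those scores discards the worst values. State that these are effects of the drug week, not of the combination with yohimbine and alcohol.
4. Optionally add end-of-session change in HAM-A and STAI-state, only where a pre-yohimbine score from the same session exists, with drinks consumed shown by condition and the self-chosen-drinking caveat stated.

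The SAP is written in the past tense and places all analysis after database lock, so label as post hoc anything added after that point.

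The cost is SAP wording, one AE comparison, one table and a few estimates, with no new data collection if the schedule holds these scores. The downside is a handful of imprecise descriptive results that must not be read as tests.
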